5.4. KRT-232 (AMG 232) + Carfilzomib, Lenalidomide, and Dexamethasone Treatment Plan

Dose Regimen

KRT-232 (AMG 232) + carfilzomib, lenalidomide, and dexamethasone will be administered per the following schedule:

Cycles 1-12 (28 day cycle)

- KRT-232 (AMG 232) once daily by mouth 7 out of 28 days
- Carfilzomib 20 mg/m² IV on Days 1 and 2 of Cycle 1, escalating to 27 mg/m² IV on Days 8, 9, 15, 16 of Cycle 1 and continuing on Days 1, 2, 8, 9, 15, 16 of Cycles 2 through Cycle 12
- Lenalidomide 25 mg PO on Days 1-21
- Dexamethasone 40 mg PO or IV on Days 1, 8, 15, and 22

Cycles 13-18 (28 days each)

- KRT-232 (AMG 232) once daily by mouth 7 out of 28 days
- Carfilzomib 27 mg/m² IV on Days 1, 2, 15, and 16
- Lenalidomide 25 mg PO on Days 1-21
- Dexamethasone 40 mg PO or IV on Days 1, 8, 15, and 22

Cycles 19+ (28 days each)

- KRT-232 (AMG 232) once daily by mouth 7 out of 28 days
- Lenalidomide 25 mg PO on Days 1-21
- Dexamethasone 40 mg PO or IV on Days 1, 8, 15, and 22

Part A (Dose-escalation scheme)

The MTD is defined as the highest dose at which six subjects have been treated and less than two subjects experienced DLT within the first cycle of treatment in Phase I of the trial. To determine the MTD, escalation for KRT-232 (AMG 232) will be conducted following the “3+3” design with de-escalation. A cohort of three subjects will be treated at the starting dose level and observed until the end of the first cycle (subjects non-evaluable for DLT will be replaced). The dose level will be escalated with each new cohort until at least one out of three subjects of a cohort experiences DLT. If one subject experiences a DLT, then three additional subjects will be treated at the same dose level; if none of the three additional subjects experiences a DLT, then the dose escalation will be continued by treating the next cohort of three subjects at the next higher dose level. If at least two out of up to six subjects at a dose level experience a DLT, the MTD will be considered to have been exceeded, and up to 3 more subjects will be treated at the next lower dose if there are less than 6 subjects already treated at that dose. The dose steps for escalation are displayed below:

Dose Escalation Schedule	
Dose Level	Dose of KRT-232 (AMG 232)*
- 1	30 mg/day PO x 7 days out of 28 day cycle
+ 1	60 mg/day PO x 7 days out of 28 day cycle
+ 2	90 mg/day PO x 7 days out of 28 day cycle
+ 3	120 mg/day PO x 7 days out of 28 day cycle

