≥ 2	Dose escalation will be stopped. This dose level will be declared the maximally administered dose (highest dose administered). Three (3) additional subjects will be entered at the next lowest dose level if only 3 subjects were treated previously at that dose.
1 out of 3	Enter at least 3 more subjects at this dose level. If 0 of these 3 subjects experience DLT, proceed to the next dose level. If 1 or more of this group suffer DLT, then dose escalation is stopped, and this dose is declared the maximally administered dose. Three (3) additional subjects will be entered at the next lowest dose level if only 3 subjects were treated previously at that dose.
≤ 1 out of 6 at highest dose level below the maximally administered dose	This is generally the recommended phase 2 dose. At least 6 subjects must be entered at the recommended phase 2 dose.

5.7. Dose Expansion Cohorts:

Once the RP2D is reached, a goal of 10 additional subjects will be treated at this dose. For the expansion cohort, subjects will continue to be monitored for occurrence of DLT. If 2 of the first 5 subjects or if ≥ 4 of 10 subjects experience DLT, the Principal Investigator will discuss with all study investigators and with CTEP whether further addition of subjects is needed to re-assess the RP2D. When the first 5 additional patients are enrolled in the expansion phase, with a total of 11 patients including the 6 patients who had been already treated at the RP2D, the probabilities of observing 3 or more patients with DLT are 22.1%, 68.7% and 96.7% if the true toxicity rate are 15%, 30%, and 50%. When all 10 additional patients are enrolled in the expansion phase, with a

total of 16 patients including the 6 patients who had been already treated at the RP2D, the probabilities of observing 5 or more patients with DLT are 7.9%, 55%, and 96.2% if the true toxicity rate are 15%, 30%, and 50%. Monitoring of all safety and toxicity data is done by the Principal Investigator and the Corresponding Organization on a real-time basis as data are entered into Medidata Rave using the Web Reporting Module. All participating sites are expected to notify the Principal Investigator when a DLT has occurred.

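### The DLT probabilities in Section 5.7 belong to a different event from the stated monitoring rule and ignore how the first six patients were selected, so the chance of flagging a toxic RP2D is overstated

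*Combined protocol and SAP*

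**What the plan says.** Section 5.7 sets the trigger on the expansion cohort: "If 2 of the first 5 subjects or if ≥ 4 of 10 subjects experience DLT". Reaching it leads to a consultation and not to an automatic stop. The lead investigator "will discuss with all study investigators and with CTEP whether further addition of subjects is needed to re-assess the RP2D".

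The next sentences give probabilities on a different base. After five expansion subjects that base is described as "with a total of 11 patients including the 6 patients who had been already treated at the RP2D". For true DLT rates of 15%, 30% and 50%, the plan says that "the probabilities of observing 3 or more patients with DLT are 22.1%, 68.7% and 96.7" percent. After ten expansion subjects the base is a "total of 16 patients including the 6 patients who had been already treated at the RP2D". At the same three rates, the plan now gives "probabilities of observing 5 or more patients with DLT are 7.9%, 55%, and 96.2" percent.

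Section 5.4 fixes what those six patients can look like: "The MTD is defined as the highest dose at which six subjects have been treated and less than two subjects experienced DLT". The count runs over Cycle 1. The decision table at the end of Section 5.6 likewise ties the recommended dose to at most 1 DLT in 6. Section 13 gives no other operating characteristics for the expansion rule.

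**The concern.** There are two separate faults.

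- **Wrong event.** The rule counts DLTs among 5 and then 10 expansion subjects. The printed probabilities count DLTs among 11 and then 16 patients, with thresholds of 3 and 5. The two agree only if exactly 1 of the first six had a DLT (3 = 1 + 2 and 5 = 1 + 4), and even then the correct probabilities are those of 2 or more in 5 and 4 or more in 10.
- **Selection ignored.** The six escalation patients are treated as a free binomial sample. By the MTD definition they have 0 or 1 DLT. The printed figures therefore include outcomes, with 2 or more DLTs in six, in which the dose would never have entered Part B.

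Confirming safety at the tentative RP2D is the only primary objective of Part B (Section 1.2.1), and these are the only figures offered for its monitoring rule. A reader at CTEP or the IRB would take from them that a dose with a 50% DLT rate is almost always flagged after five subjects, and one with a 30% rate about two times in three.

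**Working it through.** **Inputs.** True DLT rates p = 15%, 30%, 50%; trigger of 2 (read as 2 or more) of 5, or 4 or more of 10; pooled thresholds of 3 of 11 and 5 of 16 (all Section 5.7). At most 1 DLT in the six at the selected dose (Sections 5.4 and 5.6). Write q = 1 − p.

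**1. Reproduce the plan's figures.** Unconditional tails, worked at p = 50%:

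- P(X ≥ 3 of 11) = 1 − (1 + 11 + 55)/2048 = 96.7%
- P(X ≥ 5 of 16) = 1 − (1 + 16 + 120 + 560 + 1820)/65536 = 96.2%

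The same formulas give 22.1% and 68.7%, and 7.9% and 55.0%, at 15% and 30%. All six printed values are reproduced, so what was calculated is not in doubt.

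**2. The rule as written.** Let A be DLTs in the first five expansion subjects and B in the second five.

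- First look: P(A ≥ 2) = 1 − q⁵ − 5pq⁴. At 30%: 1 − 0.16807 − 0.36015 = 47.2%.
- Second look: P(A + B ≥ 4). At 50%: 1 − (1 + 10 + 45 + 120)/1024 = 82.8%.
- Either look: P(A ≥ 2) + P(A = 0)·P(B ≥ 4) + P(A = 1)·P(B ≥ 3). At 50%: 0.8125 + (1/32)(6/32) + (5/32)(16/32) = 89.6%.

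**3. The pooled event, given at most 1 DLT in six.** The 3+3 paths that lead to the MTD (0 then 0, 0 then 1, 1 then 0 in successive threes) are exactly the outcomes with at most 1 of 6. The weights are therefore those of a Binomial(6, p) restricted to 0 and 1:

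- w₀ = q/(q + 6p) and w₁ = 6p/(q + 6p). At 50%: 0.143 and 0.857. At 30%: 0.28 and 0.72.
- First look: w₀·P(A ≥ 3) + w₁·P(A ≥ 2). At 30%: 0.28 × 0.1631 + 0.72 × 0.4718 = 38.5%. At 50%: 0.143 × 0.5 + 0.857 × 0.8125 = 76.8%.
- Second look: w₀·P(A + B ≥ 5) + w₁·P(A + B ≥ 4). At 50%: 0.143 × 0.6230 + 0.857 × 0.8281 = 79.9%.

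| Event | 15% | 30% | 50% |
|---|---|---|---|
| First look: plan's figure | 22.1 | 68.7 | 96.7 |
| First look: written rule (≥ 2 of 5) | 16.5 | 47.2 | 81.3 |
| First look: ≥ 3 of 11, given ≤ 1 of 6 | 9.8 | 38.5 | 76.8 |
| Second look: plan's figure | 7.9 | 55 | 96.2 |
| Second look: written rule (≥ 4 of 10) | 5.0 | 35.0 | 82.8 |
| Second look: ≥ 5 of 16, given ≤ 1 of 6 | 3.0 | 29.4 | 79.9 |
| Either look: written rule | 17.6 | 53.6 | 89.6 |
| Either look: pooled, given ≤ 1 of 6 | 10.6 | 44.9 | 86.6 |

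**4. How much of the printed 96.7% is possible in Part B.** At 50%, P(≤ 1 of 6) = 7/64 = 0.109. Multiplied by 0.768 this is 0.084. Only 0.084 of the 0.967 comes from outcomes in which the dose could have become the MTD.

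**5. At the protocol's own limit.** Section 2.6 regards a DLT rate below 33% as acceptable. At 33% the plan's method would give 75.9% at the first look and 65.0% at the second. The written rule gives 53.2% and 43.2%; the pooled event, conditioned, gives 45.0% and 37.5%.

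**The case against.** The strongest reply is that nothing was miscalculated. The text names its events (3 or more of 11, 5 or more of 16), the tails are exact, and it never says in so many words that they are the probability of the trigger firing. That is correct as far as it goes. However, the figures follow directly on the rule and have no other purpose there, and no probability is given for the rule itself.

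Second, because Section 2.6 accepts rates below 33%, a 30% dose is not one the rule has to catch. Only 50% is clearly toxic among the three rates, and over both looks the written rule still fires 89.6% of the time. This tempers the consequence. It does not rescue the text, since 89.6% over two looks is below both single-look figures printed for 50%.

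Third, escalation already protects patients. A 50% dose passes six patients with at most 1 DLT only 10.9% of the time, and passes and is then missed at the pooled first look only 0.109 − 0.084 = 2.5% of the time. That describes escalation and monitoring together. Part B starts after the dose has been selected, so the conditional probability is the relevant one.

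Fourth, the trigger leads to a discussion rather than a stop, and DLTs are also reviewed in real time (Section 5.7) and on at least monthly calls with CTEP (Section 12.1). This stands and limits the harm. Finally, the printed figures also overstate false alarms at 15% (22.1% against 16.5%, and 7.9% against 5.0%), so the correction is not wholly unfavourable.

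**Conclusion.** The concern holds. The printed probabilities are correct tails of the wrong event, and they are wrong for Part B whether the trigger is read as expansion only or as pooled. At a 30% DLT rate each look is overstated by about 20 to 30 percentage points; at 50%, by about 13 to 20 points. For a 50% dose, the chance of no flag after five expansion subjects is 18.8% (written rule) or 23.2% (pooled, conditioned), against the 3.3% implied. Over both looks it is 10.4% or 13.4%.

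This rests on independent DLTs at a common rate, six evaluable patients at the selected dose with at most 1 DLT, and the first trigger meaning 2 or more. Taken literally as exactly 2, the first look at 50% would be only 31.3% and either look 88.7%.

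**What to change.** In Section 5.7, replace the printed probabilities with those of the rule as written, at 15%, 30% and 50%: 16.5%, 47.2% and 81.3% at five subjects; 5.0%, 35.0% and 82.8% at ten; and 17.6%, 53.6% and 89.6% for a trigger at either look. Write the first trigger as two or more of the first five.

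If the sponsor intends a pooled trigger (3 of 11, 5 of 16), the rule should be stated that way, with probabilities conditional on at most 1 DLT in the first six: 9.8%, 38.5% and 76.8%; 3.0%, 29.4% and 79.9%; and 10.6%, 44.9% and 86.6% for either look.

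The cost is wording in one section. The stated detection probabilities become less favourable and the stated false-alarm rate at 15% falls. No patients are added, and with the first option neither the thresholds nor the analysis change.

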5.8. General Concomitant Medication and Supportive Care Guidelines

5.8.1. Concomitant Medications

Because there is a potential for interaction of KRT-232 (AMG 232) with other concomitantly administered drugs, the case report form must capture the concurrent use of all other drugs, over-the-counter medications, or alternative therapies. The Principal Investigator should be alerted if the subject is taking any agent known to affect or with the potential for drug interactions. The principal investigator should be notified if the subject is taking CYP3A4 substrates with narrow therapeutic window (such as alfentanil, astemizole, cisapride, dihydroergotamine, pimozide, quinidine, sirolimus, or terfanide) or any known CYP2C8 substrates with a narrow therapeutic window while receiving AMG232.

A patient drug information leaflet and wallet card for the potential drug-interactions will be provided to each subject as referenced in Appendix B.

As noted in section 3.2.9, for treating emesis, other medications (such as fentanyl and oxycodone) may be allowed per investigator's assessment/evaluation. The study team should check a frequently-updated medical reference for a list of drugs to avoid or minimize use of.

5.8.2. Hydration

Adequate hydration is required prior to dosing of carfilzomib in Cycle 1, especially in patients at high risk of tumor lysis syndrome or renal toxicity. The recommended hydration includes both oral fluids (30 mL per kg at least 48 hours before Cycle 1, Day 1) and intravenous fluids (250 mL to 500 mL of appropriate intravenous fluid prior to each dose in Cycle 1). If needed, give an additional 250 mL to 500 mL of intravenous fluids following carfilzomib administration. Continue oral and/or intravenous hydration, as needed, in subsequent cycles. Monitor patients for evidence of volume overload and adjust hydration to individual patient needs, especially in patients with or at risk for cardiac failure.

5.8.3. Infusion Reactions

Infusion reactions, including life-threatening reactions, have occurred in patients receiving carfilzomib. Symptoms include fever, chills, arthralgia, myalgia, facial flushing, facial edema, vomiting, weakness, shortness of breath, hypotension, syncope, chest tightness, or angina. These reactions can occur immediately following or up to 24 hours after administration of carfilzomib. Dexamethasone will be administered will be required as a premedication during Cycle 1 prior to carfilzomib infusion to reduce the incidence and severity of infusion reactions (See Section 5.7). Subjects will be informed about risk and of symptoms and to contact a physician immediately if symptoms of an infusion reaction occur.

5.8.4. Blood Pressure Monitoring

Hypertension, including hypertensive crisis and hypertensive emergency, has been observed with carfilzomib. Some of these events have been fatal. Monitor blood pressure regularly in all patients. If hypertension cannot be adequately controlled, withhold carfilzomib and evaluate. Consider whether to restart carfilzomib based on a benefit/risk assessment.

5.9. Treatment Duration

In the absence of treatment delays due to adverse event(s), treatment may continue until one of the following criteria applies:

- Disease progression by IMWG criteria (Appendix 15.6).
- Unacceptable adverse event(s) defined as:
 - Occurrence of an AE that is related to treatment with the study drug which, in the judgment of the investigator, compromises the subject's ability to continue study-specific procedures, or is considered to not be in the subject's best interest.
 - Persistent AE requiring a delay of therapy for more than 4 weeks (28 days)
- Subject decides to withdraw from the study
- Pregnancy
 - All women of child bearing potential should be instructed to contact the investigator immediately if they suspect they might be pregnant (e.g., missed or late menstrual period) at any time during study participation.
 - The investigator must immediately notify CTEP in the event of a confirmed pregnancy in a subject participating in the study.
- Termination of the study by sponsor
- The drug manufacturer can no longer provide the study agent
- Subject achieves complete remission (CR), and the subject and investigator feel that discontinuation of KRT-232 (AMG 232) + KRd is in the subject's best interests, or
- Subject achieves a level of response that qualifies him or her for another therapy, such as high dose therapy with autologous stem cell transplantation, and the subject and investigator feel that discontinuation of KRT-232 (AMG 232) + KRd is in the subject's

best interests

The reason(s) for protocol therapy discontinuation, the reason(s) for study removal, and the corresponding dates must be documented in the Case Report Form (CRF).

5.10. Duration of Follow Up

Subjects will be followed for 30 days after removal from study or until death, whichever occurs first. Subjects removed from study for unacceptable adverse event(s) will be followed until resolution or stabilization of the adverse event.

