Study Duration:	Subjects will receive KRT-232 (AMG 232) + KRD at a dose defined by the treatment outline above. This therapy will be continued without a cap on the number of allowed cycles, unless one of the following occurs: 
• Disease progression by IMWG criteria (Appendix 15.6).• Unacceptable adverse event(s) defined as:
◦ Occurrence of an AE that is related to treatment with the study drug which, in the judgment of the investigator, compromises the subject's ability to continue study-specific procedures, or is considered to not be in the subject's best interest.◦ Persistent AE requiring a delay of therapy for more than 4 weeks (28 days)• Subject decides to withdraw from the study• Pregnancy
◦ All women of child bearing potential should be instructed to contact

	
the investigator immediately if they suspect they might be pregnant (e.g., missed or late menstrual period) at any time during study participation.
 
○ The investigator must immediately notify CTEP in the event of a confirmed pregnancy in a subject participating in the study.● Termination of the study by sponsor● The drug manufacturer can no longer provide the study agent● Subject achieves complete remission (CR), and the subject and investigator feel that discontinuation of KRT-232 (AMG 232) + KRd is in the subject's best interests, or● Subject achieves a level of response that qualifies him or her for another therapy, such as high dose therapy with autologous stem cell transplantation, and the subject and investigator feel that discontinuation of KRT-232 (AMG 232) + KRd is in the subject's best interests 
At the completion or early discontinuation of treatment, subjects will be followed for an additional 30 days after the last administration of treatment or up until the initiation of the next line of treatment, whichever comes first. Subjects with adverse events until the event has resolved or the condition has stabilized.

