
Descriptive statistics will be provided for selected demographic, safety, PK, and PD data by dose and time as appropriate. Descriptive statistics on continuous data will include means, medians, standard deviations, and ranges, while categorical data will be summarized using frequency counts and percentages. Graphical summaries of the data may be presented.
 
A full pharmacokinetic profile of KRT-232 (AMG 232) will be proposed in this protocol to assess exposure-response relationships with various PD endpoints (i.e., MIC-1 changes, toxicity, efficacy). KRT-232 (AMG 232) concentrations in these samples will be quantitatively measured using liquid chromatography/tandem mass spectrometric (LC/MS/MS) method that will be developed by the Analytical Pharmacology Core Laboratory at the Sidney Kimmel Comprehensive Cancer Center (SKCCC) at Johns Hopkins. For KRT-232 (AMG 232), the individual PK parameters from a single dose will be estimated for C_{max}, AUC, $T_{1/2}$, apparent Cl/F, and apparent V/F using non-compartmental or compartmental PK methods with the software WinNonlin. For serum MIC-1 levels, each individual level will be normalized to the baseline level for that subject. Advanced population PK methods may be employed to assess the link between drug exposure and biological effects and efficacy. The PK variables and changes in MIC-1 will be tabulated and descriptive statistics (e.g., geometric means and coefficients of variation) calculated for each dose level. PK parameters (i.e., $T_{1/2}$, Cl, and AUC) and MIC-1 changes will be compared across dose level using nonparametric statistical testing techniques. Exploratory correlative studies with pharmacodynamic (biological endpoints, toxicity and efficacy) will be analyzed using nonparametric statistics. Significance for comparisons will be at the $p < 0.05$ level.
 
Efficacy analysis will be performed for all subjects in the dose escalation and dose expansion part of the study. Separate efficacy analyses will be performed on the full analysis set which includes all subjects enrolled on study, and the primary analysis set which includes only subjects who were biomarker positive (TP53 WT). Parameters assessed will include minimal residual disease (MRD) negative, stringent complete response (sCR), complete response (CR), very good partial response (VGPR), and partial response (PR), minimal response (MR), and stable disease (SD) per IMWG Uniform Response criteria. In addition, overall response rate (defined as greater than or equal to PR across all cycles of treatment), response duration, time-to-response (TTR), PFS, and OS will be assessed.
 
Best overall response categories will be tabulated by dose cohort and overall for the IMWG categories of MRD-negative, sCR, CR, VGPR, PR, MR, SD, progressive disease, and relapse. A two-sided 95% exact binomial CI will be calculated for each category. The myeloma response rate (responses \geqPR) will also be tabulated by dose cohort and overall. Time-to-event analyses will be done using Kaplan-Meier analyses and will include time to response, duration of response, progression-free survival (PFS), and overall survival (OS), as data allow. If there is not enough data to apply the Kaplan-Meier test, the data will be summarized by descriptive statistics.

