An adverse event is considered serious if it results in **ANY** of the following outcomes:

Death

A life-threatening adverse event

An adverse event that results in in subject hospitalization or prolongation of existing hospitalization for ≥ 24 hours

A persistent or significant incapacity or substantial disruption of the ability to conduct normal life functions

A congenital anomaly/birth defect.

Important Medical Events (IME) that may not result in death, be life threatening, or require hospitalization may be considered serious when, based upon medical judgment, they may jeopardize the subject or subject and may require medical or surgical intervention to prevent one of the outcomes listed in this definition. (FDA, 21 CFR 312.32; ICH E2A and ICH E6).

ALL SERIOUS adverse events that meet the above criteria **MUST** be immediately reported to the NCI via electronic submission within the timeframes detailed in the table below.

Hospitalization	Grade 1 and Grade 2 Timeframes	Grade 3-5 Timeframes
Resulting in Hospitalization ≥ 24 hrs	10 Calendar Days	24-Hour 5 Calendar Days
Not resulting in Hospitalization ≥ 24 hrs	Not required	

NOTE: Protocol specific exceptions to expedited reporting of serious adverse events are found in the Specific Protocol Exceptions to Expedited Reporting (SPEER) portion of the CAEPR.

Expedited AE reporting timelines are defined as:

“24-Hour; 5 Calendar Days” - The AE must initially be submitted electronically within 24 hours of learning of the AE, followed by a complete expedited report within 5 calendar days of the initial 24-hour report.

“10 Calendar Days” - A complete expedited report on the AE must be submitted electronically within 10 calendar days of learning of the AE.

¹Serious adverse events that occur more than 30 days after the last administration of investigational agent/intervention and have an attribution of possible, probable, or definite require reporting as follows:

Expedited 24-hour notification followed by complete report within 5 calendar days for:

All Grade 3, 4, and Grade 5 AEs

Expedited 10 calendar day reports for:

Grade 2 AEs resulting in hospitalization or prolongation of hospitalization

²For studies using PET or SPECT IND agents, the AE reporting period is limited to 10 radioactive half-lives, rounded UP to the nearest whole day, after the agent/intervention was last administered. Footnote "1" above applies after this reporting period.

Effective Date: May 5, 2011

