10. STUDY CALENDAR

10.1. Part A: Dose Escalation

Cycle (a)	Pre-Cycle	Cycle 1			Cycle 2	Cycle 3-12	Cycle 13-18	Cycle 18+	Post-Cycle
Visit Number	1	2	3	4	5	TBD	TBD	TBD	TBD
Visit Description	Screening	Exam and 1 st dose	Exam	Exam	Exam	Exam	Exam	Exam	EOT (b)
Cycle Day(s)	-28 to 0	1	8	15	1	1	1	1	ND
Visit Window (days)			+/-2	+/-2	+/-4	+/-4	+/-4	+/-4	+/-5
KRT-232 (AMG 232)		A			A	A	A	A	
Carfilzomib		B1			B1	B1	B2		
Lenalidomide		C			C	C	C	C	
Dexamethasone		D			D	D	D	D	
Informed Consent	X								
Demographics	X								
Medical History (c)	X								
Adverse events	X	X	X	X	X	X	X	X	X
Prior/concomitant medications	X	X	X	X	X	X	X	X	X
ECOG performance status	X	X	X	X	X	X	X	X	X
Vital signs	X	X	X	X	X	X	X	X	X
Height	X	X							
Physical Exam, including weight (c)	X	X	X	X	X	X	X	X	X
CBC with diff, platelets	X	X (d)	X	X	X (e)	X (e)	X (e)	X	X
Serum chemistries (f)	X	X (d)	X	X	X (g)	X (g)	X (g)	X	X
aPTT, PT, and INR	X								
Hepatitis panel (h)	X								
Urine or serum β-HCG (i)	X	X	X	X	X	X	X	X	X
Myeloma laboratory assessment (j)	X	X			X	X	X	X	X
Bone marrow aspiration and biopsy (k)	X				X (l)				X (l)
TP53 status (NGS)	X								
Blood sample for drug exposure measurement (m)		X				a			
MIC-1 serum sample (n)	X	X							
Buccal mucosal swab	X								
Blood sample for banking (o)	X								
Myeloma bony survey (p)	X								
Echocardiogram	X								
Dispense KRT-232 (AMG 232)		X			X	X	X	X	X
Pill diaries dispensed/reviewed		X	X	X	X	X	X	X	X

A: KRT-232 (AMG 232), dose as assigned, Day 1 through D7

B1: Carfilzomib 20 mg/m² IV on Days 1 and 2 of Cycle 1, escalating to 27 mg/m² IV on Days 8, 9, 15, 16 of Cycle 1 and continuing on Days 1, 2, 8, 9, 15, 16 of Cycles 2 through Cycle 12

B2: Carfilzomib 27 mg/m² IV on Days 1, 2, 15, and 16

C: Lenalidomide 25 mg PO on Days 1-21

D: Dexamethasone 40 mg PO or IV on Days 1, 8, 15, and 22

- a. Each cycle will last 28 days. Cohort safety assessment for DLTs will be performed after Day 28 of Cycle 1.
- b. End-of-Treatment Visit will occur 30 (\pm 5) days after the last administration of KRT-232 (AMG 232). If the subject begins another form of anticancer therapy before the end of the 30 (\pm 5)-day period, every effort will be made to complete all the End-of-Treatment assessments prior to commencing the new therapy. If there is an abnormality in need of monitoring beyond the End-of-Treatment Visit, subjects will be followed until resolution or confirmed stability of the abnormality.

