11. MEASUREMENT OF EFFECT

11.1. Multiple Myeloma Response Assessment

Although the clinical benefit of KRT-232 (AMG 232) has not yet been established, the intent of offering this treatment is to provide a possible therapeutic benefit in combination with KRD, and thus the subject will be carefully monitored for tumor response and symptom relief in addition to safety and tolerability. Subjects with measurable disease will be assessed by standard criteria. Responses levels, including MRD-negative, sCR, CR, VGPR, PR, MR, SD, and progressive disease will be determined by the IMWG Uniform Response Criteria as per Appendix F (Kumar et al., 2016). For the purposes of this study, subjects should be re-evaluated for response every 4 weeks. In addition to a baseline myeloma laboratory testing, confirmatory myeloma laboratory assessment will also be obtained within 4 weeks following initial documentation of an objective response.

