PFS will be calculated as the time from the time of enrollment until documented disease progression, as determined by the Investigator using IMWG uniform response criteria, or death from any cause, whichever occurs first. Kaplan-Meier methods will be used to estimate PFS over time and the median duration of PFS. Subjects with no PFS event will be censored at the date of their last myeloma disease assessment.

OS is defined as the time from the initial administration of KRT-232 (AMG 232) + KRd to death from any cause. Kaplan-Meier methods will be used to estimate the OS function. Subjects who do not die will be censored at the date that the subject was last known to be alive.

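### Kaplan-Meier overall survival is planned, but no routine vital-status collection is scheduled beyond about 30 days after last treatment or study removal, so any OS curve reported could be biased upward

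*Combined protocol and SAP*

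**What the plan says.** **OS analysis.** Section 13.6 runs OS from first dose to death from any cause. It states "Kaplan-Meier methods will be used to estimate the OS function" and "Subjects who do not die will be censored at the date that the subject was last known to be alive". Section 13.6 and the synopsis (Statistical Considerations) both list "progression-free survival (PFS), and overall survival (OS), as data allow", and both fall back to descriptive statistics if data are too few for Kaplan-Meier.

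**End of follow-up.** Section 5.10: "Subjects will be followed for 30 days after removal from study or until death, whichever occurs first". The synopsis (Study Duration) has subjects "followed for an additional 30 days after the last administration of treatment or up until the initiation of the next line of treatment", whichever is first. In both calendars (10.1 and 10.2) the last column is the End-of-Treatment visit, which footnote b times at 30 (±5) days after the last KRT-232 dose. There is no survival or vital-status row.

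**Sources of later data.** Unresolved adverse events or abnormalities are followed to resolution or stability (synopsis, 5.10, footnote b). Subjects removed for *TP53* status continue toxicity follow-up (3.2.2, 5.1). Under section 7.3, late reporting covers serious events that "occur more than 30 days after the last administration of investigational agent/intervention and have an attribution of possible, probable, or definite require reporting".

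**Link to progression.** Section 5.9 lists progression first among the reasons to stop treatment. Under section 11.1, "subjects should be re-evaluated for response every 4 weeks".

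**The concern.** Kaplan-Meier treats a censored subject as having the same later risk of death as those still under observation. Here routine contact stops because the subject has left treatment, most often at progression. Subjects still at risk for OS are then largely those who have not progressed, and deaths after progression mostly go unseen. If the death hazard is higher after progression than before it, the estimated curve lies above the true one.

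At stake is a secondary descriptive result that could be read as ordinary overall survival. A confidence interval shows sampling error; it does not show this bias.

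**Working it through.** **Reading the texts together.** The documents give no OS rate or expected number of deaths, so there is no planned figure to reproduce. Take a subject whose last treatment is dexamethasone on Day 22 and whose progression is found on Day 29. Under the synopsis, follow-up ends on Day 22 + 30 = Day 52, which is 23 days after progression, or earlier if a new line starts. Under 5.10 it ends 30 days after study removal, whenever that is recorded. Lags of 0, 1 and 3 months cover next-line therapy at once, the usual case, and late removal.

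**Inputs.**
- Median PFS 26.3 months: section 2.4.3, the KRd arm of the cited phase 3 trial, without KRT-232.
- Share *q* of PFS events that are deaths: 10-20% (assumed).
- Median post-progression survival *m*: 6, 12 or 24 months (assumed).
- Exponential times (assumed).

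**Formulas.** λ = ln 2/26.3 = 0.02636 per month and μ = ln 2/*m*.
- True OS(t) = e^(−λt) + (1−q)·λ·(e^(−λt) − e^(−μt))/(μ−λ).
- With censoring L months after progression, the hazard that Kaplan-Meier estimates at u ≥ L is (qλ + μr)/(1+r), where r = (1−q)·λ·(1 − e^(−(μ−λ)L))/(μ−λ). For u < L, replace L by u. With L = 0 the curve is e^(−qλt).

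**One cell in full** (q = 10%, m = 12, L = 1, t = 12):
- e^(−12λ) = 0.7289, e^(−12μ) = 0.5000 and λ/(μ−λ) = 0.02636/0.03141 = 0.839.
- True OS = 0.7289 + 0.9 × 0.839 × 0.2289 = 0.902.
- r = 0.9 × 0.02636 × 0.9845 = 0.02335. Hazard = (0.002636 + 0.05776 × 0.02335)/1.02335 = 0.00389.
- Cumulative hazard = 11 × 0.00389 + about 0.0033 for month 1 = 0.0461. The curve is e^(−0.0461) = 0.955.
- Overstatement: 95.5 − 90.2 = 5.3 points.

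**All cells, 12-month OS (%), 1-month lag.**

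| q | m (months) | True | Kaplan-Meier | Difference |
|---|---|---|---|---|
| 10% | 6 | 85.6 | 94.1 | 8.5 |
| 10% | 12 | 90.2 | 95.5 | 5.3 |
| 10% | 24 | 93.3 | 96.2 | 2.9 |
| 20% | 6 | 84.2 | 91.5 | 7.3 |
| 20% | 12 | 88.2 | 92.7 | 4.5 |
| 20% | 24 | 91.0 | 93.3 | 2.3 |

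With no lag the differences are 2.8-11.3 points; with 3 months, 1.4-4.7. Simulation agrees to about 0.1 point. If 10-30% of subjects also leave in response by 12 months (assumed), the 1-month range is 1.8-8.5.

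**Direction.** The bias is zero when μ = qλ, that is m = 26.3/q: 263 months (q = 10%) or 131.5 months (q = 20%). It is upward for any shorter post-progression survival.

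**Against sampling error.** Section 13.3 gives 25-40 subjects and two accrual rates, 1.5 and 2.5 per month. The earliest section 13.2 analysis is n/rate + 6 months: 25/1.5 + 6 = 22.7, 40/1.5 + 6 = 32.7, 25/2.5 + 6 = 16.0 and 40/2.5 + 6 = 22.0. By simulation with uniform entry and a 1-month lag:
- 7-23 subjects are at risk at 12 months, and the 95% half-width is 6.5-13 points.
- The bias exceeds the half-width in 2 of 24 cells (8.5 against 8.0, and 8.5 against 8.3).
- Deaths counted, of all deaths by the analysis, in the same order: 1.0-2.2 of 2.2-4.9; 1.9-4.4 of 5.4-11.1; 0.8-1.8 of 1.5-3.5; 1.5-3.5 of 3.4-7.7. Some 31-71% go uncounted.

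Subjects removed for *TP53* mutation (3-8% in section 9.1.1, about 1-3 of 25-40) are not modelled.

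**The case against.** The strongest reply is that this is a phase 1 safety study, where short follow-up is a legitimate choice. OS is not among the objectives in section 1 and informs no dose decision, stopping rule or sample size. The OS analysis is qualified by data availability, and with so few deaths the descriptive fallback may well apply. The censoring rule limits neither the source nor the date of survival information, and some later data will come from the adverse-event and *TP53* follow-up. The bias is mostly no larger than sampling error.

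Most of that stands, and it sets the weight of the point. It does not remove it. The availability clause and the fallback address sparse data, have no threshold, and do nothing about censoring tied to progression. The censoring rule permits later vital status, but nothing requires anyone to collect it. The later data cover selected subjects only: a myeloma death some months after progression, with no open adverse event and no attribution to treatment, falls under none of these sources.

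A reader might also infer three things that the documents do not support:
- That follow-up has three conflicting ends. Footnote b times one visit and provides for longer monitoring of abnormalities. The conflict is between the synopsis and 5.10, with a visit anchored to a third date.
- That progression is itself removal from study. Section 5.9 records stopping therapy and study removal as separate items with their own dates, so censoring soon after progression follows directly only from the synopsis.
- That a curve resting on 1-4 deaths will be reported. It could be, and that count is a product of the assumptions above.

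**Conclusion.** The point holds as a low-priority matter to consider. Followed as written, the plan ties OS censoring to leaving treatment, chiefly at progression, and any OS curve could be biased upward if the risk of death rises after progression. The documents do not state that it does; this is an assumption, and the break-even values show how long post-progression survival would have to be for it to fail.

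The size at 12 months is about 2-9 points with a 1-month lag, 3-11 with none and 1-5 with 3 months. It rests on a PFS median borrowed from another regimen and on assumed values for the rest.

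Larger distortions at 24 or 36 months might be inferred from the same model, but the trial's timing does not support claiming them. At the earliest analysis, 24 months is reached in only one of the four accrual scenarios (40 subjects at 1.5 per month), with about 7 at risk and a half-width of 12-17 points.

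**What to change.** Choose one:

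- **(a) Give up OS as such.** In section 13.6 and the synopsis, replace Kaplan-Meier OS with counts of deaths on study or within 30 days, or relabel the curve as on-study survival and state the limitation. This costs wording only; the trial then reports no overall survival.
- **(b) Keep OS.** Amend 5.10, the synopsis and both calendars so that vital status is recorded by chart or phone for every treated subject up to the section 13.2 analysis cut-off. This costs a few contacts for up to about 40 subjects.

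Separately, and whichever is chosen, reconcile the end-of-follow-up statements in the synopsis and section 5.10, and align the End-of-Treatment visit anchor in footnote b of both calendars with the result. In the Day 29 example, that visit falls due on Day 7 + 30 = Day 37 (32-42), while the synopsis follows the subject to Day 52.
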